Vascular outcomes: Arterial stiffness will be assessed by measuring right radial artery waveforms by high-fidelity micromanometer (SPC-301; Millar Instruments) and central aortic pressure waveforms (SphygmoCor, AtCor Medical Systems, Sydney, Australia) after a euglycemic clamp. Systemic arterial stiffness will be determined by the augmentation index (AIx), which is calculated as the difference between the second systolic peak and inflection point, expressed as a percentage of the central pulse pressure and corrected to an average heart rate of 75 beats/min. Aortic pulse wave velocity will be measured by sequentially recording ECG-gated right carotid and radial artery waveforms. Our group has extensively used this methodology in prior studies of participants with diabetes⁸¹. Sympathetic nervous system activity will be measured by heart rate variability using methods previously described by our group (SphygmoCor, Atcor Medical Systems Inc., Sydney, Australia). Cardiac output, stroke volume and total peripheral resistance will measured using the Non-Invasive Cardiac Output Monitoring (NICOM® system Cheetah Medical Inc.).

Renal outcomes: Renal function will be assessed using serum creatinine in order to calculate the estimated GFR (CKD-EPI equation). GFR will also be measured in the supine position using the gold-standard iohexol clearance technique, standardized per 1.73m² body surface area. Both eGFR and measured GFR are included in this study as the eGFR is the renal parameter that is utilized in

clinical practice, and provides information on what eGFR change could be expected with dapagliflozin therapy clinically. In addition, the eGFR is also a safety measure that is followed in clinical practice.

Markers of oxidative stress, including 8-hydroxydeoxyguanosine and 8-isoprostane will be measured in plasma and urine using an ELISA assay (Eve technologies, Calgary, Alberta). Albuminuria will be assessed by measuring urine albumin excretion from a 24-hour urine collection. Natriuresis will be assessed with a 24-hour urine collection for sodium excretion. In addition, fractional lithium excretion (FELi), fractional sodium excretion (FENa) and renal segmental tubular Na+/Li+ clearances will also be measured to study the SGLT2i-related natriuresis mechanisms and localization of sodium excretion in the renal tubule. This methodology has been described in detail elsewhere in our previous work^{82, 83}.

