## 2. Secondary objectives:

2.1. We will characterize the safety of dapagliflozin use compared to placebo.

We will determine acute and chronic effects of dapagliflozin vs. placebo from baseline on:

- 2.2. Calcineurin inhibitors (CNI) levels, a class of immunosuppressants measured by tacrolimus or cyclosporine
- 2.3. Systemic hemodynamics
- 2.4. Total and proximal renal tubular natriuresis measured by sodium/lithium clearance
- 2.5. Sympathetic nervous system (SNS) activation
- 2.6. Metabolic parameters
- 2.7. Kidney function indicated by iohexol-measured and estimated glomerular filtration rate (GFR)
- 2.8. Neurohormones
- 2.9. Glucose-lowering effects

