#### 2. Outcomes for the secondary objectives:

- 2.1. Safety will be assessed by the number of hypoglycemic episodes, acute rejection episodes, volume depletion, UTI or genital infection, acute kidney injury, ketoacidosis and serious adverse events.
- 2.2. CNI levels will be measured by tacrolimus or cyclosporine levels
- 2.3. Systemic hemodynamic assessments include the following group of outcomes:
  - a. NICOM parameters (chronic change only)
  - b. arterial stiffness
    - *i.* radial, aortic and carotid augmentation index (AIx)
    - *ii.* carotid-radial pulse-wave velocity (PWV)
    - iii. carotid-femoral PWV
- 2.4. Natriuretic effect will be measured using the following group of outcomes:
  - a. Lithium clearance
    - *i.*  $FE(Li^+) = 100 X ([(urine Li^+) X (creatinine plasma)]/[(plasma Li^+) X (creatinine urine)]$
  - b. Total overall (proximal and distal) tubular sodium handling
    - *i.*  $FE(Na^+) = 100 X ([(urine Na^+) X (creatinine plasma)]/[(plasma Na^+) X (creatinine urine)]$
  - c. Distal sodium handling:
    - $i. \quad FE(Na^+) FE(Li^+)$
- 2.5. SNS activation will be measured by norepinephrine, epinephrine, dopamine, heart rate and heart rate variability (RMSSD and SDNN).
- 2.6. Metabolic parameters will be measured by weight and waist circumference Lipid profile will be measured by cholesterol, LDL, HDL and triglyceride (use screening instead of baseline value).
- 2.7. Renal hemodynamic function will be measured using the following groups of outcomes:
  - a. Iohexol measured GFR
    - i. mGFR
    - *ii. Hematocrit (HCT)*
  - b. 24 hour urine measured GFR
    - *i.* 24-hour Creatinine (mmol/day)
    - *ii.* Creatinine clearance (ml/min)
  - c. Estimated GFR (eGFR) calculated by CKD-EPI 2021 equation
- 2.8. Neurohormones will be measured by plasma aldosterone and plasma renin concentration

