2.9. Glucose-lowering effect will be measured by HbA1c and fasting blood glucose

# 3. Outcomes for the exploratory objectives:

- 3.1. Plasma volume will be estimated [ePV] by Strauss estimation:
  - a.  $([{Hb_{baseline}/Hb_{end}} \times {(100-Ht_{end})/(100-Ht_{baseline})}]-1) \times 100$
- 3.2. Relationship between proximal renal tubular natriuretic effects and volume reduction: proximal renal tubular natriuretic effects will be evaluated by lithium clearance FE(Li+); volume change will be measured using the following outcome:
  - a. Estimated plasma volume (ePV)
    - *i.* Estimated percent change by Strauss estimation
  - $([{Hb_{baseline}/Hb_{end}} \times {(100 Ht_{end})/(100 Ht_{baseline})}] 1) \times 100$
- 3.3. Relationship between proximal renal tubular natriuretic effects and kidney function: proximal renal tubular natriuretic effects will be evaluated by lithium clearance FE(Li+); Kidney function will be measured using measured GFR.
- 3.4. Relationship between volume and SNS activation: Volume will be measured by ePV. Hormones will be measured by:
  - a. Neurohormones: Plasma aldosterone and renin
  - b. SNS markers: norepinephrine, epinephrine, dopamine, heart rate, heart rate variability (SDNN and RMSSD)
- 3.5. Relationship between neurohormones and volume markers with kidney function. Hormones will be measured by serum aldosterone and renin. Volume will be measured by ePV. Absolute measure of renal function outcomes is measured by measured GFR.
- 3.6. Relationship between arterial stiffness and neuro-hemodynamic & volume markers. Arterial stiffness outcomes will be measured by radial, aortic and carotid AIx, carotid-radial PWV and carotid-femoral PWV. Neuro-hemodynamic and volume markers will be measured by:
  - a. Seated: SBP, DBP, and MAP
  - b. NICOM: SBP, DBP, and MAP (chronic change only)
  - c. SNS: epinephrine, norepinephrine, dopamine, heart rate, heart rate variability (SDNN and RMSSD)
  - d. Neurohormones: Plasma aldosterone and renin
  - e. Volume will be measured by ePV
- 3.7. Relationship between neurohormones & volume markers and blood pressure. Hormones will be measured by plasma aldosterone and renin. Volume will be measured by ePV. Seated and NICOM (chronic change only) measures of SBP, DBP, and MAP will be the blood pressure outcomes.
- 3.8. The blood and urine biomarkers are:
  - a. Plasma chemistry:
    - *i.* Sodium, potassium, urea, phosphate, chloride, calcium
    - ii. AST, ALT, ALP, amylase

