# 2. Analysis for secondary objective:

- 2.1. The numbers of hypoglycemic episodes, acute rejection episodes, volume depletion, UTI or genital infection, acute kidney injury, ketoacidosis and serious adverse events will be reported for both the placebo group and dapagliflozin group. No statistical comparisons will be performed.
- 2.2. 2.10. The same models described in the analysis of primary objective 1.1 will be completed for each of the different outcomes.

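### SAP outcome 2.4c, read as FE(Na) minus FE(Li), is not scaled to distal delivery, so it mostly follows the proximal marker and cannot by itself localise sodium handling

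*Protocol*

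**What the plan says.** Protocol 9.1.2 (Renal outcomes) gives the purpose of the lithium and sodium measurements: "renal segmental tubular Na+/Li+ clearances will also be measured to study the SGLT2i-related natriuresis mechanisms and localization of sodium excretion in the renal tubule". It gives no formula and refers to earlier work for the method.

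The formulas are in the SAP, Outcomes for the secondary objectives, item 2.4:

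- 2.4a is FE(Li), built from "urine Li^+) X (creatinine plasma" over the matching plasma lithium and urine creatinine terms. Elsewhere the SAP takes it as the proximal marker: "proximal renal tubular natriuretic effects will be evaluated by lithium clearance FE(Li"+).
- 2.4b is FE(Na), described as "Total overall (proximal and distal) tubular sodium handling".
- 2.4c is "Distal sodium handling", formed from FE(Na) and FE(Li).

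Secondary objective 2.4 itself names only "Total and proximal renal tubular natriuresis measured by sodium/lithium clearance". For the secondary outcomes from 2.2 on, the analysis section says: "The same models described in the analysis of primary objective 1.1 will be completed for each of the different outcomes". P-values for secondary objectives are nominal. Neither document scales distal handling to distal delivery, says how to read the sign of 2.4c, or gives expected FE values.

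The sign between the two terms of 2.4c is not legible in the extracted text. A minus is the best reading: dashes are lost elsewhere in the SAP (the item ranges 2.2 to 2.10 and 3.2 to 3.7), while the slashes in the two formulas just above 2.4c survive.

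**The concern.** FE(Li) stands for the share of filtered sodium that leaves the proximal tubule, and FE(Na) for the share that is excreted. Their difference is the amount handled in between, as a share of filtered load. That amount rises whenever more sodium is delivered, even if the distal tubule reabsorbs the same fraction of what it receives.

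The SAP's exploratory hypotheses (3.2, 3.3) expect a proximal effect of dapagliflozin, so FE(Li) is expected to move. Item 2.4c would then move with it, under a distal label. A reader could take a significant 2.4c as a distal drug effect, or as distal compensation, when it may show neither. The stated aim, "localization of sodium excretion in the renal tubule", needs a measure that stays still when only the proximal tubule changes.

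**Working it through.** **The plan's own figure.** The documents give no value for FE(Na), FE(Li) or their difference. The only stated figure used here is the size in Protocol 5.3. With a difference of 6.5 mmHg, SD 8, two-sided alpha 0.05 and 80% power, n per arm = 2 x (1.96 + 0.84)^2 x 64/42.25 = 23.8, so 24 per arm and 48 in total, as stated (power 0.804, normal approximation).

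**Algebra (no assumed values).** Let q = FE(Na)/FE(Li), the fraction of delivered sodium that escapes distal reabsorption. Then

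D = FE(Na) - FE(Li) = -(1 - q) x FE(Li).

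When q is small, D is close to -FE(Li). D is also a linear combination of 2.4a and 2.4b, so its treatment effect is essentially effect(b) minus effect(a).

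**Range of FE(Na).** Take sodium excretion equal to the diet target (150 mmol/day in Protocol 9.3, 140 in the Table 2 footnote; the two should be reconciled, but the choice does not matter here). Assume plasma sodium of 140 mmol/L. FE(Na) = intake / (GFR x 1.44 L/day x 140):

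- GFR 30 (the eGFR limit in Protocol 5.1): 140 to 150 / 6048 = 2.3-2.5%
- GFR 45: 140 to 150 / 9072 = 1.5-1.7%
- GFR 60: 140 to 150 / 12096 = 1.2%
- GFR 90: 140 to 150 / 18144 = 0.8%

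**Size of D.** With FE(Li) assumed at 10-40%, q runs from 0.8/40 = 0.02 to 2.5/10 = 0.25. So D lies between -0.98 and -0.75 times FE(Li). The tie is loosest near GFR 30.

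**Worked cases, starting at FE(Na) 1.2% and FE(Li) 20% (q = 0.06, D = -18.8).**

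- Proximal only, q fixed: FE(Li) 25, FE(Na) 1.5, D = -23.5. Change -4.7, with distal fractional reabsorption unchanged at 94%.
- Proximal with full distal compensation: FE(Li) 25, FE(Na) 1.2, D = -23.8. Distal fractional reabsorption rises to 1 - 1.2/25 = 95.2%.
- Distal only: FE(Li) 20, FE(Na) 1.8, D = -18.2. Change +0.6, about 3% of its size.

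The first two cases are different mechanisms, yet D differs between them by 0.3 points.

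**Simulation.** 24 per arm; baseline-adjusted comparison standing in for the SAP mixed model; 1,500 runs per scenario. Assumed: FE(Na)/FE(Li) of 1.2/20, 1.2/30, 2.5/15 and 2.5/30; CV 30% for FE(Li) and 50% for FE(Na); within-person correlation 0.5; FE(Na)-FE(Li) correlation 0 or 0.5. Share of trials significant:

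| Scenario | D (2.4c) | log q |
|---|---|---|
| Proximal only, FE(Li) x1.25 or x1.4 | 62-99% | 4-7% |
| Distal only, FE(Na) x1.5 | 6-26% | 82-97% |

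FE(Na) alone detects the distal-only effect in 86-89%. The correlation of D with -FE(Li) is 0.99 or higher at 1.2/20 and 1.2/30, about 0.99 at 2.5/30 and about 0.955 at 2.5/15.

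**Compensation.** For FE(Li) x1.4 at 1.2/30, 2.5/15 and 2.5/30, D is significant in 94-99% of trials without compensation and in 99% or more with FE(Na) held flat. Log q is significant in 5-7% and 64-89%. For x1.25 at 1.2/20, with the CV of the ratio assumed at 45%, the figures are 82% and 87% for D, and about 5% and 53% for the ratio.

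**The case against.** **The SAP already analyses FE(Li) and FE(Na) separately.** This stands for a distal-only effect. FE(Na) would rise with FE(Li) unchanged, and FE(Na) alone finds a x1.5 effect in about 79-89% of simulated trials, depending on the variability assumed. A reader might infer that the plan as a whole would miss a distal effect or mislocate it; the documents do not support that. The argument is weaker when FE(Li) moves, as the SAP expects. Under a proximal-only x1.25 effect, FE(Na) is itself significant in only about 40% of trials, so a flat FE(Na) beside a raised FE(Li) is poor evidence of compensation. No listed outcome tests it directly.

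**The difference is a valid quantity.** This stands. If more sodium arrives and more is reabsorbed, distal handling as a share of filtered load has changed. The fault is offering it as the distal measure with no scaling to delivery and no stated reading of its sign.

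**The controlled diet undermines the proximal-only scenario.** If sodium balance is restored by week 12, FE(Na) returns to about baseline at similar GFR, and a sustained rise in FE(Li) then means real distal compensation. That is a fair account of what may happen. But the ratio's rejections in that case (about 50% at x1.25) are correct detections, while D is significant almost as often without compensation.

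**Little depends on 2.4c.** This stands. Objective 2.4 does not name the distal segment, the association analyses (3.2, 3.3, 5.2) use FE(Li), and p-values are nominal.

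**Conclusion.** The point holds for one secondary mechanistic outcome. Read as a difference, 2.4c is dominated by FE(Li), responds to a purely proximal effect, is insensitive to a change in distal fractional reabsorption, and barely separates a proximal effect with distal compensation from one without. By itself it does not serve the localisation aim.

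The algebra is free of assumptions. The sizes are not: they rest on FE(Li) of 10-40%, FE(Na) derived from the diet, and assumed CVs and correlations, none of which the documents state. Nor do the documents support reading 2.4c as identical to FE(Li) with the same p-value. Near the eGFR limit the two diverge: at 2.5/15 with uncorrelated FE(Na) and FE(Li), a proximal-only x1.25 effect is significant in 62% of trials for 2.4c and 82% for FE(Li). The conclusion also depends on the operator being a minus. The primary systolic blood pressure analysis is unaffected.

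**What to change.** Confirm the operator in SAP 2.4c. If it is a minus:

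1. Add distal fractional reabsorption as the measure of distal handling: 100 x (1 - FE(Na)/FE(Li)) = 100 x (1 - (urine Na x plasma Li)/(plasma Na x urine Li)). Creatinine cancels. Analyse it with model 1.1, preferably as log[FE(Na)/FE(Li)].
2. If the difference is kept, label it as distal reabsorption in percent of filtered load with negative sign, and state that a change in it is not by itself evidence of a distal drug effect.

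Cost: one derived variable from values already measured, a line or two of SAP text, and one more nominal p-value at each time point. No new samples.

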9.2 Randomization, blinding and treatment allocation

The randomization scheme will be computer-generated by an independent biostatistician. To achieve a balance of participants in each arm, permuted block randomization will be used with variable blocks of 4 and 6. Randomization will be stratified based on T2D and PTDM status, as the effects of dapagliflozin may differ between these two groups. Participants will be randomized only after screening and informed consent has been obtained. All participants, nurses, physicians, study coordinators and investigators will be blinded to the treatment allocation. In addition, all participants, study personnel and study sponsor will be blinded until the end of the trial to all the laboratory and test results obtained during the trial. Dapagliflozin and placebo tablets, as well as drug packaging will be identical in appearance. Adherence to the intervention will be determined using pill counts and questioning of participants at each study visit⁸⁷. Reasons for non-adherence and drug discontinuation will be ascertained.

9.3 Study procedures

Leading up to week 0, 1 and 12, participants will be placed on a 7-day diet targeting 150 mmol/day Na⁺ and ≤ 1.5 g/kg/day protein, verified with a 24-hour urine sample to measure Na⁺ and urea excretion prior to all experiments. This moderate, fixed dose Na⁺ and moderate protein diet avoids the confounding effect of circulating volume contraction and renin-angiotensin-aldosterone system activation due to low Na⁺ diets, and the renal hyperfiltration effect of high protein intake⁸⁸. An electrocardiogram will also be performed at the screening visit. At 22:00 on the night prior to the study day, all participants will take 300 mg of lithium carbonate (Li⁺CO₃) to derive renal segmental tubular Na+/Li+ clearances the following day, as described previously^{82, 83}. Week 0, 1 and 12 studies will start at 0745 hours, and participants will fast for the duration of the day. All studies will be performed under clamped euglycemic conditions (capillary blood glucose 4 to 6 mmol/L) to avoid confounding effects of hyperglycemia on blood pressure and renal function. After clamped euglycemia is achieved for approximately 2-4 hours, blood samples will be collected for makers of oxidative stress (8-isoprostane and 8-hydroxydeoxyguanosine). Sympathetic nervous system activation will be assessed using heart rate variability^{89, 90}. Following blood and urine tests, blood pressure will be assessed using an automated vital signs monitor (Connex Vital Signs Monitor, Welch Allyn) at 60-minute intervals. Baseline arterial stiffness (SphygmoCor, Atcor Medical Systems Inc., Sydney, Australia) will be measured non-invasively using applanation tonometry using standard techniques that we have used previously^{72, 73}. Cardiac output, stroke volume and total peripheral resistance will be derived from stroke volume and heart rate that is measured using the Non-Invasive Cardiac Output Monitoring (NICOM® system Cheetah Medical Inc.) that we have also used previously⁹¹. GFR (per 1.73 m²) will be measured in

the supine position using iohexol clearance⁷¹. Participants will then be randomized to dapagliflozin 10 mg PO daily or a placebo. Identical studies will be performed at study weeks 0, 1 and 12, with the exception of NICOM, which will be performed on study weeks 0 and 12 only. All procedures will be supervised by a study physician.

Serum, plasma and urine will be collected and stored on study weeks 0,1, and 12 for potential future analyses for exploratory biomarkers to assess relationships with disease activity and effects of study drug. After completion of the study, samples will be stored into a secure central storage facility at Toronto General Hospital. Those results may be pooled with biomarker data from other similar studies to generate hypotheses to be tested in future research. Potential biomarkers to be measured include but are not limited to electrolytes, natriuretic peptides, markers of inflammation/fibrosis, metabolomics and urinary vesicles.

9.4 Withdrawal of individual subjects

Subjects can leave the study at any time for any reason if they wish to do so without any consequences. The investigator can decide to withdraw a subject from the study for urgent medical reasons.

9.5 Reasons for possible drug discontinuation

- 1. Serious adverse events or an intolerable adverse effect such as a persistent allergy or rash;
- 2. Clinically significant persistent changes from baseline based on laboratory safety assessments;
- 3. Pregnancy or breastfeeding;
- 4. Withdrawal of consent;
- 5. Participant unable to adequately complete study visits or procedures.

9.6 Replacement of individual subjects after withdrawal

Patients that meet inclusion criteria will be invited for participation in the study. When patient agrees to participate in the study, informed consent is signed. When patient decides to withdraw after start of the treatment period, new patients can be admitted to the study to reach the required sample size.

9.7 Follow-up of subjects withdrawn from treatment

Subjects who withdraw from the study will be followed up according to the routine terms of patient care at the outpatient clinic. Subjects will be followed up until resolution of the inciting adverse event responsible for drug withdrawal. If withdrawal was unrelated to an AE, then subjects will be followed up approximately 10 days after drug discontinuation for an end of treatment visit with

repeat bloodwork from the time of screening. In case of withdrawal of consent, participants will not be contacted nor followed by the study team.

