5.3 Sample Size

The sample size is based on the primary endpoint of blood pressure. Currently, there is only one publication from our group with information available on the effect of SGLT2i on blood pressure reduction in KTR with diabetes. In this observational study of 10 KTR and simultaneous pancreas-kidney transplant recipients treated with canagliflozin, we reported a SBP decrease of $6.5 \pm 10 \text{ mmHg}^{63}$. Given the small sample size in our observational study, we believe the standard deviation would be smaller in a larger cohort. Blood pressure reduction with SGLT2 inhibition appear to be similar between patients with and without diabetes in non-transplant studies. We, therefore, estimated the sample size based on a SBP change of 6.5 mmHg with a standard deviation of 8 mmHg. Under the hypothesis that SGLT2i decreases SBP by $6.5 \pm 8 \text{ mmHg}$ compared to placebo with a two-sided alpha of 0.05 and 80% power, we calculate a sample size of n=48, with 24 randomized to dapagliflozin and 24 randomized to placebo. Assuming a 10% attrition rate, the final sample size required is 52 participants. This sample size is similar to those successfully used in previous studies⁷¹, and sufficient to measure secondary renal endpoints related to renal hemodynamic function⁷¹, natriuresis and arterial stiffness⁷²⁻⁷⁴. Based on previous studies, we anticipate an even sex distribution in each group.

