10.5 Suspected unexpected serious adverse reactions (SUSARs)

Adverse reactions are all untoward and unintended responses to an investigational product related to any dose administered. Unexpected adverse reactions are SUSARs if the following three conditions are met:

- 1. the event must be serious;
- 2. there must be a certain degree of probability that the event is a harmful and an undesirable reaction to the medicinal product under investigation, regardless of the administered dose;
- 3. the adverse reaction must be unexpected, that is to say, the nature and severity of the adverse reaction are not in agreement with the product information as recorded in:
 - Summary of Product Characteristics (SPC) for an authorised medicinal product;
 - Investigator's Brochure for an unauthorised medicinal product.

Health Authority and METC Reporting

SUSARs will be reported to the accredited ethics committee and recorded in an overview list. When needed, they will be also reported expedited to the appropriate health authority (Health Canada).

In an emergency, unblinding can be performed to identify the treatment given to that subject. Unblinding is not to be performed for any reason, other than an emergency where unblinding is required. When the Investigator unblinds the subject he/she must note the date, time and reason for removing it and record this information in the Comments section of the CRF and in the source data. He/she must also immediately inform the project leader/principal investigator about the unblinding of the subject treatment. Even though the subject has been unblinded, any blood samples for safety or pharmacodynamic assessments will continue to be drawn, for at least 24hr following the last dose as long as doing so will not compromise subject welfare. It is the responsibility of the Principal Investigator to ensure the investigator site staff are appropriately

trained on the unblinding procedure in case of emergency. Study drug must be discontinued after unblinding but the subject will be followed until resolution of the adverse event. It is the intent that subjects who discontinue treatment with the study drug will continue in the study according to the visit schedule. At the conclusion of the study, the occurrence of any unblinding can be reported.

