#### 5. Pre-specified post-hoc analyses:

- 5.1. The same models described in the analysis of primary objective 1.1 will be performed for the outcome.
- 5.2. The same models described in the analysis of exploratory objective 3.2 will be completed for each of the different outcomes.

Analysis population: The intention to treat population will be used for all analyses.

*Hypothesis testing:* For hypothesis testing, a 5% significance level will be used (two-sided). No interim analyses will be performed. For secondary objectives, nominal p-values will be reported.

*General model assumptions and model diagnostic procedures:* For the linear mixed-effects models with visit and treatment-by-visit interaction as covariates, a participant-level random intercept will be included. Restricted-maximum-likelihood will be used for estimation and the missing-at-random framework will be assumed. Plots of marginal and conditional residuals will be used for model diagnostics and assessment. Similar diagnostic procedures will be used for the linear regression models.

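### Protocol sections 9.7 and 10.5 conflict on whether participants who stop study drug early are followed to the 12-week blood pressure that the ITT analysis needs.

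*Protocol*

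**What the plan says.** **Follow-up after stopping drug.** The heading of Protocol section 9.7 concerns withdrawal from treatment, but its first sentence concerns leaving the study and gives routine clinic care. It then sets out two routes. Stops caused by an adverse event are followed until that event resolves. Stops for other reasons are "followed up approximately 10 days after drug discontinuation for an end of treatment visit". A closing sentence deals separately with withdrawn consent and rules out further contact. Visit 9 is not mentioned.

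**The contrary statement.** Section 10.5, in its text on emergency unblinding, gives as the intent that "subjects who discontinue treatment with the study drug will continue in the study according to the visit schedule".

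**Replacement.** Under section 9.6, when a patient decides to withdraw after treatment has begun, "new patients can be admitted to the study to reach the required sample size".

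**Analysis.** Protocol section 11 sets the primary comparison at 12 weeks, specifies intention-to-treat and keeps non-adherent patients in. The SAP's closing section agrees: "The intention to treat population will be used for all analyses". SAP analysis 1.1 fits the chronic change to Visits 3 and 9 only. The model has a participant random intercept, is estimated by REML and assumes missing at random.

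**Sample size.** Section 5.3 uses an "SBP change of 6.5 mmHg with a standard deviation of 8 mmHg" and a "two-sided alpha of 0.05 and 80% power". This gives 48 participants, "with 24 randomized to dapagliflozin and 24 randomized to placebo". It then adds: "Assuming a 10% attrition rate, the final sample size required is 52 participants".

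**The concern.** Stopping a drug and leaving a trial are different events. An intention-to-treat comparison at 12 weeks needs the 12-week outcome from people who stopped the drug but still consent. Section 9.7 runs the two events together and offers those people no route to Visit 9. Section 10.5 would keep them on schedule, but it is phrased as an intent and sits in the SUSAR section. A site looking up drug discontinuation would go to sections 9.5 to 9.7.

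The chronic model has no intermediate data to fall back on. Section 9.1.1 measures blood pressure at weeks 1 and 6, but neither value enters the model. A participant without Visit 9 supplies a baseline alone, so the missing-at-random assumption conditions on little more than baseline pressure and arm. Volume depletion (including hypotension) and urinary and genital infection are adverse events of interest in section 10.2.3, and any of them could plausibly lead to stopping. Missingness related both to the drug and to blood pressure is therefore a realistic possibility. Neither document states a sensitivity analysis to the assumption. A week-12 reading that was never taken cannot be recovered at analysis.

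**Working it through.** **1. Whom section 9.7 covers.** Three features show that it reaches participants who stop drug but still consent: its heading, its reference to an end-of-treatment visit timed from drug discontinuation, and its separate sentence for withdrawn consent.

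| Situation | Section 9.7 | Section 10.5 |
|---|---|---|
| Stops drug because of an adverse event | Followed until the event resolves | Intended to stay on the visit schedule |
| Stops drug for another reason | One visit about 10 days later | Intended to stay on the visit schedule |
| Withdraws consent | No contact | Not addressed |

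The first two rows conflict. Table 2 combines Visit 10 with an early end-of-study visit that includes vital signs. An off-drug pressure might be recorded there, but it is not a Visit 9 value and does not enter the chronic model.

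**2. The plan's sample size.** Inputs from section 5.3: difference 6.5 mmHg, SD 8 mmHg, two-sided alpha 0.05, power 80%.

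n per arm = 2 × (1.960 + 0.842)² × 8² / 6.5² = 23.8, so 24 per arm and 48 in total. This reproduces the plan. Power at 24 per arm is 80.4% (normal approximation) or 78.7% (noncentral t).

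Allowance for 10% attrition:
- 48 / 0.90 = 53.3
- 48 × 1.10 = 52.8
- the plan states 52
- 52 × 0.90 = 46.8 expected to remain, slightly below 48; at 23.4 per arm, power is 79.4% (normal approximation)

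The stated 52 is close enough not to be an issue in itself. It does mean that the 52 does not fully absorb a 10% loss.

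**3. Possible bias (illustration).** Bias in the arm mean = fraction without Visit 9 × (true value − value implied by the model). Two inputs are assumed, not taken from the documents as results: 10% of the dapagliflozin arm has no week-12 value, and those values would be 3 to 10 mmHg worse than predicted.
- 0.10 × 3 = 0.3 mmHg, and 0.3 / 6.5 = 5% of the target
- 0.10 × 10 = 1.0 mmHg, and 1.0 / 6.5 = 15% of the target

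With these inputs the shift favours the drug. If the missing values were better than predicted, the sign would reverse. No offsetting loss in the placebo arm is assumed.

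**4. What collecting the values does.** Off-drug values then count, so the estimate is the effect of assignment. Assume that 10% of the dapagliflozin arm is off drug at week 12 with no residual effect. The expected difference is 6.5 × 0.90 = 5.85 mmHg. With 26 per arm and SD 8, power = Φ(5.85 / (8 × √(2/26)) − 1.96) = 75.1%, against 83.4% if the full 6.5 mmHg held in all 52. This is the power for the quantity that an ITT analysis claims to estimate.

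**The case against.** The strongest reply is that section 9.7 can be read as a rule for people who leave the study, as its first sentence suggests. On that reading it is compatible with 10.5, and section 11 already keeps non-adherent patients in the analysis. The wording does allow this reading, and it should temper the claim. It does not remove the conflict, because the heading, the terms for stopping drug and the separate consent sentence all point to participants who could still attend Visit 9.

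Several stronger readings are tempting, and the documents do not support them:

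- **That week-12 pressure is not collected after an early stop.** Section 9.7 does not forbid Visit 9, and 10.5 would retain it. The supportable statement is that 9.7 does not provide for it.
- **That everyone who stops goes to the 10-day visit.** That visit is only for stops unrelated to an adverse event. The adverse-event route is different, though it names no Visit 9 either.
- **That ITT has no data behind it for discontinuers.** Participants with only a baseline remain in the REML model under missing at random. The SAP's acute comparison at week 1 is untouched by a later stop.
- **That withdrawals are replaced and dropped.** Section 9.6 is permissive and is triggered by the patient's decision to withdraw. Nothing removes the replaced person from the ITT set; the documents simply do not address the point.
- **That 9.6 is redundant because attrition is already in the 52.** It is not: 52 × 0.90 = 46.8, below the planned 48.

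It is also fair to object that the 10% allowance covers all losses. Some of those will be withdrawn consent, which no wording can recover.

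**Conclusion.** The point holds as an inconsistency with consequences for the primary endpoint. Section 9.7 gives consenting participants who stop drug early no route to Visit 9, 10.5 states the opposite intent, and the 12-week ITT model depends on that visit. A site following 9.7 as written could lose primary-outcome data permanently. The affected participants would stay in the model with a baseline only, and the estimate would lean on missing at random. Replacement under 9.6 would not repair that.

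The size is uncertain. A shift of about 0.3 to 1.0 mmHg against the 6.5 mmHg target rests wholly on the assumed 10% missing in the dapagliflozin arm and the assumed 3 to 10 mmHg departure, and its direction rests on those values being worse than predicted. It shows scale and is not a forecast. No figure stated in the plan is shown to be wrong. The change is worth making because it is cheap and works only if made during the trial.

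**What to change.** 1. Reconcile sections 9.7 and 10.5 so that stopping study drug is defined separately from leaving the study, with one statement of follow-up for each. This concerns outcome collection only and leaves the reasons for stopping drug untouched.
2. State that Visit 9 seated systolic pressure is sought from every randomised participant who has not withdrawn consent, on or off drug, and that it enters the ITT model.
3. State in 9.6 that anyone admitted is additional and that the replaced participant stays in the ITT set. Do not delete 9.6 on the ground that attrition is already covered.

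For values that remain missing, a prespecified analysis that shifts the implied values over a stated range would be a useful addition to the SAP.

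The cost is protocol wording and a few Visit 9 blood pressure measurements already in the schedule. On the trial's own allowance this is at most about five (52 × 0.10 = 5.2), and fewer where consent is withdrawn.
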